3) Inclusion and Exclusion Criteria***A. Inclusion Criteria**

To be eligible participants should:

- Diagnosed with HIV (based on self-report).
- Be 18 years and older
- Have smoked ≥ 5 cigarettes/day in the past year

- Be interested in making a quit attempt in the next 30 days
- Own a smartphone (apple/android), and plan to keep it active for the next 6 months
- Able to consent
- Have no plans to move in the next 6 months
- Are not pregnant or planning to be pregnant in the following 6 months
- Have any condition that, in the opinion of the investigator, would compromise the well-being of the patient or the study or prevent the patient from meeting or performing study requirements

B. Exclusion Criteria

Participants would be excluded if they:

- Have contraindication to NRT (past month myocardial infarction, history of serious arrhythmias/or unstable angina pectoris, dermatological disorder)
- Are currently being treated for a psychiatric condition.
- Are currently being treated for smoking cessation, alcoholism, or illicit drug use
- Are adults unable to consent
- Are individuals who are not yet adults
- Are pregnant women
- Are prisoners

4) Study Design

- a. Study Type – Interventional
- b. Primary Purpose – Other
- c. Interventional Study Model – Sequential
- d. Number of Arms – 2
- e. Randomized or not – Randomized
- f. Open label or if blinded – Not blinded
- g. Number of participants – 100

5) Procedures Involved*

We will recruit participants via community and clinic flyers and among participants of another on-going survey who smoke (IRB#20180269). In Stage 1, participants will be randomized into one of two groups: 1) a group mindfulness training (MT) for smoking cessation, or 2) contingency management (CM) for smoking cessation. In Stage 2 non-

responders (those who have not quit at 1 month evaluation) will be randomized to: 1) *Switch* to sequentially receive the other intervention (i.e., CM or MI) and complete the 3-month assessment; or 2) *Continue* without further intervention and complete the 3-month assessment only.

In stage 1, both groups will do the following:

- Complete a baseline survey.
- Receive 6 weeks of Nicotine Replacement Treatment (NRT) via mail
- Receive reminder/encouragement calls or texts the day before their quit date and 2 weeks after their quit date.

Arm 1: The MT smoking cessation intervention:

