Participants will attend an orientation session via Zoom or in person to introduce them to mindfulness, smoking cessation, and what is covered in the group sessions. This orientation will last 60-90 minutes. They will receive twice weekly group sessions (eight total during 4 weeks) via Zoom or in person that were manualized and will be delivered in Spanish or English by a Hispanic instructor(s) experienced in MT (a single therapist with >4 years of training in MT). We will e-mail participants study materials ahead of the first group session, such as the participant study booklet. We will also communicate with participants using WhatsApp to send them reminders and links to mindfulness recordings.

The overarching theme of momentary awareness and acceptance of cravings and affect (e.g., stress, anxiety etc.) will be introduced and reinforced in complementary ways throughout the training. Each session will last 45-60 minutes.

- a. *Session (1):* Will introduce participants to the concept of how smoking can become a habituated behavior triggered by an environmental, physical, or mental stimulus through associative learning. It also will explore how cravings feel in the body and how MT can help individuals become more aware of these processes.
- b. *Session (2):* Will examine how thoughts, emotions and body sensations become triggers for craving and smoking and introduce a technique to ‘mindfully’ work with cravings (Recognize, Accept, Investigate and Note what cravings feel like as they arise; acronym: RAIN).
- c. *Session (3):* Will introduce how difficult emotions perpetuate smoking as well as a standard meditation technique called loving-kindness as a way to work with them. Loving-kindness is practiced through directed well wishing, typically by repetition of phrases such as ‘may X be happy.’
- d. *Session (4) (quit date):* Will teach participants how cravings thwart long-term goals, and reinforce mindfulness techniques as a way to help individuals disengage from habitual responding and realign with their goals.
- e. *Session (5):* Will introduce participants to mindfulness practice in everyday life, including “awareness of breath” meditation and mindful walking (“four modes of walking”), during which individuals practice systematically noting

objects that they see, and then objects that they hear, then objects that they smell, and then tactile objects such as the pressure of their feet on the ground).

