Participants in this arm will attend an orientation session via Zoom that will last 60-90 minutes. They will connect with a research associate 3 times per week for 3 weeks after quit date via zoom where they will answer a few questions about their quitting progress, report on past 7-day smoking, and provide a sample of CO to verify their smoking status after their quit date using a portable CO monitor (coVita iCO™ Smokerlyzers®) and/or NicoTests saliva screen test that has been mailed to them. Those who proved their abstinence (CO< 8 ppm using coVita iCO™ Smokerlyzers®) and/or 30 ng/mL using NicAlert) [14] will receive a cash reward. The first successful CO sample earns \$5 cash, and then the reward increases by \$2 for each consecutive successful CO and/or saliva sample (e.g., \$5, \$7, \$9...). Participants also earn \$2 bonus for 4 consecutive successful CO and/or saliva samples (total=\$4). In all, participants can earn a maximum of \$176. Participant who fail the CO and/or saliva test will not receive reinforcement and the value of the next payment will be reset to the one that was missed.

Figure (1): overview of the study design

All participants will be asked to complete an end of treatment assessment 2 weeks after the intervention ends, which will be the same as the 3-month follow-up described below. Breath CO and/or saliva sample test (for cotinine analysis) will be collected at the end of treatment assessment via Zoom for participants who report they have quit.

All participants will be asked to complete a follow-up assessment 3 months after their quit date to assess their smoking status as well as get information about concomitant smoking and NRT use, use of additional NRT or cessation drugs (e.g., bupropion), and use of other tobacco methods. Breath CO and/or saliva sample test (for cotinine analysis) will be collected at the 3-month follow-up points for participants who report abstinence. The breath sample will be collected with the portable CO monitor (coVita iCO™ Smokerlyzers®) and/or NicoTests saliva screening test. A cut-off of 8 ppm for CO test (using coVita iCO™ Smokerlyzers®) and/or ≤ 30 ng/mL for the saliva sample test (using NicoTests) will be used to determine abstinence (Benowitz et al 2002).

Study measures

1. Baseline Assessment: All study materials and instrument will be translated into Spanish.

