- *Demographics and HIV history:* Age, race/ethnicity, birth origin, years in USA, relationship status, education, employment, income, acculturation, discrimination, self-identity, time since HIV diagnosis, HIV treatment.

Smoking status will be verified using breath carbon monoxide (CO [< 8 parts per million (ppm)], which can be determined quickly through a small, hand-held monitor and/or using a saliva screening test (cutoff concentration of ≤ 30 ng/mL), which can be determined quickly through a NicoTests saliva sample.

- *Smoking:* Smoking history, past quit attempt, motivation to quit, confidence in quitting, Fagerström test for nicotine dependence,^[15] 12-item smoking self-efficacy to resist urge to smoke,^[16] and 15-item Minnesota nicotine withdrawal scale (i.e., craving, irritability, anxiety, depression).^[17]

- *Mindfulness skills:* The 15-item short form five facets of mindfulness questionnaire that measures MT skills related to observing, describing, acting with awareness, non-judging of inner experience, and non-reactivity to inner experience.^[18]

- *Others:* The 20-item Centers for the Epidemiologic Study of Depression (CES-D) scale,^[19] social support,^[20] quality of life,^[21] and alcohol and substance use (ASSIST).^[22]

2. End-of treatment assessment (one month after quit date):

- The follow up assessment will occur at 1 months after quit date. The visit will last approximately 45 minutes.

- Information on number of sessions that was attended.

- *Acceptability:* The acceptability will be assessed by 3 items “How satisfied were you with the intervention?”, “How likely are you to recommend this intervention to a friend?” and “How useful was the intervention?”

Smoking Cessation: Main smoking cessation outcome is 7-day point-prevalence abstinence (defined as self-report of not smoking in the past 7-days; not even a puff) and confirmed smoking cessation by expired carbon monoxide (CO) level cutoff of < 8 ppm using a coVita iCO™ Smokerlyzer® and/or NicoTests saliva sample of ≤ 30 ng/mL at the 1-month follow up. Secondary outcomes include the reduction in number of cigarettes smoked per day.^[23,24] Relapse is defined as smoking at least once/week on two consecutive weeks.^[25] These are described in more detail below.

3. Three-month Follow-up Assessment (3-month after quit date):

- The follow up assessment will occur at 3 months (+30 days) after quit date. The visit will last approximately 45 minutes.

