- All baseline assessment will be re-administered except demographics.

- Information on number of sessions that was attended.
- *Acceptability:* The acceptability will be assessed by 3 items “How satisfied were you with the intervention?”, “How likely are you to recommend this intervention to a friend?” and “How useful was the intervention?”
- *Smoking Cessation:* Main smoking cessation outcome is 7-day point-prevalence abstinence (defined as self-report of not smoking in the past 7-days; not even a puff) and confirmed smoking cessation by expired carbon monoxide (CO) level cutoff of < 8 ppm using a coVita iCO™ Smokerlyzer® and/or NicoTests saliva sample of ≤ 30 ng/mL at the 3-month follow up. Secondary outcomes include the reduction in number of cigarettes smoked per day.[23,24] Relapse is defined as smoking at least once/week on two consecutive weeks.[25] These are described in more detail below.
- *Process evaluation:* Semi-structured post-intervention evaluation interviews will be conducted with randomly selected participants to further inform our assessment of acceptability and perceived helpfulness of interventions, and identifying key areas for refining the intervention protocols (e.g., improving access, content, usability). These will be conducted in-person or via Zoom and participants will receive \$25 for completing the interview.

Primary Outcome Measure Title: Smoking cessation - 7-day point-prevalence abstinence.

Outcome Measure Description:

Defined as self-report of not smoking in the past 7-days, not even a puff and confirmed by expired carbon monoxide (CO) level cutoff of < 8 ppm using a coVita iCO™ Smokerlyzer® and/or NicoTests saliva sample of ≤ 30 ng/mL.

Outcome Measure Timeframe:

4 weeks (end of treatment), and 3 months

Secondary Outcomes

1. Treatment-specific retention rates for study measures.
 - Defined as: Percentage of participants completing all study procedures divided by total enrolled. Coded reasons for dropouts.
 - Timeframe: 3 months
2. Treatment-specific adherence rates to study protocol
 - Defined as number of phone-call check-ins attended by each participant (4 for mindfulness training, 12 for contingency management).
 - Timeframe: 3 months

6) Data and Specimen Banking*

There will be no data or specimen banking.

7) Data Management*

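### The end-of-treatment visit has two timing rules that cannot both hold in the contingency management arm; the one tied to intervention end puts that arm about 5 to 7 days later after quitting than mindfulness training

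*Combined protocol and SAP*

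**What the plan says.** Two places in the combined protocol and SAP set the time of the end-of-treatment visit.

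- Section 5 (Procedures Involved), in the text after Figure 1: "All participants will be asked to complete an end of treatment assessment 2 weeks after the intervention ends". This counts from the end of the intervention.
- Study measures, item 2: the heading reads "End-of treatment assessment (one month after quit date", and its first bullet repeats "The follow up assessment will occur at 1 months after quit date". This counts from the quit date. It gives one time, names no arm and states no window.

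The visit has two uses. It is the first time point of the primary outcome, whose timeframe is "4 weeks (end of treatment), and 3 months" with no starting point named. It also appears to be the evaluation that drives Stage 2, where non-"responders (those who have not quit at 1 month evaluation) will be randomized to" switch or continue.

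The arms run on different schedules. For MT, "They will receive twice weekly group sessions (eight total during 4 weeks", and the fourth session is marked "Session (4) (quit date". For CM, Section 5 schedules three Zoom contacts a week for 3 weeks after the quit date. By contrast, the later visit has both an anchor and a window: "The follow up assessment will occur at 3 months (+30 days) after quit date".

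**The concern.** The two programmes end at different times after quitting: about 2 weeks in MT and about 3 weeks in CM. A rule that counts from the end of the programme therefore assesses the arms at different times since quitting, while a rule that counts from the quit date does not. Staff could follow either sentence in good faith.

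The outcome is abstinence over the preceding 7 days, so a shift of several days means that the arms are judged on largely different post-quit days. A comparison of MT with CM at this visit would then mix treatment with time since quitting. So would the responder label, which is the tailoring variable of the SMART. With no window for this visit, nothing in the text limits further drift.

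**Working it through.** **Inputs**

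- MT: 8 sessions, two per week over 4 weeks, quit date at Session 4 (Section 5, Arm 1).
- CM: 3 contacts per week for 3 weeks after the quit date (Section 5, Arm 2).
- Rule A: intervention end + 14 days (Section 5).
- Rule B: one month after the quit date, taken as 28 to 31 days (Study measures, item 2).
- Assumption: 'the intervention' is the MT or CM programme, not the 6 weeks of nicotine replacement that both arms receive.

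**Step 1. MT under rule A.** Session 4 is the second session of week 2 and Session 8 the second session of week 4. On any fixed pair of weekdays they are 14 days apart.

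Visit day = 14 + 14 = 28.

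This reproduces one month (28 to 31 days), and also 4 weeks if counted from the quit date. The rules do not conflict in MT.

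**Step 2. Number of CM contacts.** 3 × 3 = 9. The stated maximum payment of $176 can be used as a check. Nine escalating rewards from $5 to $21 total 9 × (5 + 21)/2 = $117. Adding the $4 bonus and the $20, $10 and $25 assessment payments:

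117 + 4 + 20 + 10 + 25 = $176.

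This matches. Twelve rewards from $5 to $27 would total 12 × (5 + 27)/2 = $192, already above the maximum. The payment schedule therefore supports nine contacts over 3 weeks.

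**Step 3. CM under rule A.** Counting the full 3 weeks, the programme ends on day 21 and the visit is on day 21 + 14 = 35. Counting from the ninth contact needs a weekday pattern, which the protocol does not give. With Monday/Wednesday/Friday assumed and the first contact after the quit date, the ninth contact falls on day 19, 20 or 21, depending on the weekday of quitting.

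Visit day = 19 + 14 to 21 + 14 = 33 to 35.

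Under that pattern, day 32 (18 + 14) arises only if the participant quits on a Monday and has the first contact the same day.

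**Step 4. Comparison** (look-back is the 7 days ending on the visit day)

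| | Visit day | Look-back days | Days shared with MT |
|---|---|---|---|
| MT, rule A | 28 | 22–28 | – |
| CM, rule A, earliest | 33 | 27–33 | 2 (days 27, 28) |
| CM, rule A, latest | 35 | 29–35 | 0 |

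Gap between arms: 33 − 28 = 5 to 35 − 28 = 7 days. CM would also be 33 − 31 = 2 to 35 − 28 = 7 days beyond one month, so rule A cannot satisfy rule B in this arm.

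**Step 5. Both arms on day 28 after the quit date.** The look-back is days 22–28 in both arms, so all 7 days are shared. Days since last treatment contact: MT 28 − 14 = 14; CM 28 − 21 = 7 to 28 − 19 = 9.

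**The case against.** The best defence is that the discrepancy comes from one sentence and affects one arm. The Stage 2 rule and both statements under Study measures agree on one month, so most readers would follow them. Rule A also has a rationale: it equalises time since treatment ended at 14 days in both arms, which a quit-date anchor gives up. In a pilot that allows 30 days at the 3-month visit, a shift of under a week at the interim visit is modest. Section 7 (Data Management) names an abstinence model only for 3-month cessation, and that visit is tied to the quit date wherever it is described. Within a Stage 1 arm, the Switch and Continue groups share the same timing, so their contrast is not distorted by an offset between arms.

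Most of this stands, and it limits the point to a modest one. It does not remove the contradiction in CM. The end-of-treatment time point is a declared primary-outcome time point, and responder status is settled at this stage.

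Three stronger readings are tempting but unsupported:

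- *That the rules also conflict in MT.* Day 28 is a legitimate month. A discrepancy appears only if one month is fixed at exactly day 30, which the protocol does not do.
- *That the later CM visit biases abstinence against CM because there is more time to relapse.* The documents give no abstinence or relapse rates, so neither size nor direction can be derived.
- *That CM adherence can reach only 9 of 12, or 75%.* The adherence outcome refers to 12 phone-call check-ins, and Section 5 describes 9 Zoom contacts. The text does not say that they are the same. This is a separate question and has no bearing on the visit timing in Section 5.

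**Conclusion.** The concern holds for the CM arm. Followed as written, the Section 5 sentence puts the CM visit at about day 33 to 35 after quitting, against day 28 in MT. The gap is about 5 to 7 days, with 0 to 2 of 7 look-back days in common. The figure is 7 days with no overlap if the full 3 weeks are counted. A gap of 4 days, with 3 days shared, requires a first CM contact on the quit day itself.

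The result rests on reading the intervention as the behavioural programme. It also rests, for the lower end of the range, on the assumed Monday/Wednesday/Friday pattern. The nicotine replacement reading is less plausible: if the 6 weeks began on the quit date (the start is not stated), the visit would fall on day 42 + 14 = 56, far from one month in either arm.

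This should be corrected because it concerns a primary-outcome time point and the Stage 2 decision. No effect on abstinence is shown, and the timing of the 3-month outcome is unaffected.

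**What to change.** 1. In Section 5, replace the timing that counts from the end of the intervention with: 4 weeks (day 28) after the Stage 1 quit date in both arms, with the same stated window. Day 28 is the best choice because it already satisfies the Section 5 rule in MT, the one-month rule and the 4-week timeframe.
2. In the primary outcome timeframe, state that the 4 weeks are counted from the quit date.
3. For participants already assessed, report the actual assessment day after the quit date by arm.
4. Separately, and only as a clarification, state whether the 12 CM check-ins in the adherence outcome are the 9 Zoom contacts in Section 5. If they are, use 9.

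The cost is protocol wording and date fields in REDCap, with no added visits. The downside is that time since last treatment contact becomes unequal, 14 days in MT and about 7 to 9 days in CM, so it should be reported by arm alongside the abstinence results.

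### At 1 month, saliva cotinine alone may confirm abstinence while study nicotine patches may still be in use, and no rule covers patch users

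*Combined protocol and SAP*

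**What the plan says.** All references are to the combined protocol and SAP.

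- **Outcome.** In section 5, Study measures, item 2 (end-of-treatment assessment), abstinence is self-report of no smoking for 7 days, confirmed by CO below 8 ppm "and/or NicoTests saliva sample of ≤ 30 ng/mL at the 1-month follow up". The primary outcome definition uses the same alternative, at 4 weeks and 3 months.
- **Collection.** Section 5 states: "Breath CO and/or saliva sample test (for cotinine analysis) will be collected at the end of treatment assessment", from those who report having quit. On cut-offs, 8 ppm for CO and/or 30 ng/mL "for the saliva sample test (using NicoTests) will be used to determine abstinence".
- **Nicotine replacement.** Section 5 (Stage 1) mails both groups a six-week supply. Section 8 (Risks to Subjects) describes it as transdermal patches. The start day is not given.
- **NRT use.** The 3-month assessment is to "get information about concomitant smoking and NRT use". Participants also complete "an end of treatment assessment 2 weeks after the intervention ends, which will be the same as the 3-month follow-up", so the question carries over to 1 month by that cross-reference. The list under item 2 does not name it, and the answer does not enter the abstinence definition.
- **CM sessions.** Participants connect "3 times per week for 3 weeks after quit date" and "provide a sample of CO to verify their smoking status". A CO monitor and/or a "NicoTests saliva screen test that has been mailed to them" is mentioned here. No equivalent mailing is described for MT.

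Nowhere does the plan require CO at the 1-month visit, say which test prevails if the two disagree, or make provision for someone using nicotine replacement.

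**The concern.** Cotinine is formed from nicotine whatever its source. This is general pharmacology rather than a statement in the documents. A saliva cut-off therefore cannot tell a smoker from an abstinent person wearing a patch that the study supplied. CO does not respond to patch nicotine.

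A visit at which only saliva is collected complies with the plan as written. At such a visit a participant who has stopped smoking and uses the patches can fail verification. The 1-month abstinence rate is a primary outcome, and this error moves it in one direction only. Status at 1 month also selects the non-responders who are randomised again in Stage 2.

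**Working it through.** The plan gives no expected quit rate, power calculation, patch adherence or cotinine distribution, so there is no planned figure to reproduce. The checks concern classification, timing and a range of sizes.

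**1. Classification.** Take an abstinent patch user with CO below 8 ppm and saliva cotinine above 30 ng/mL.

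| How the alternative is applied | Classed as |
|---|---|
| CO only | abstinent |
| Both taken, either pass suffices | abstinent |
| Saliva only | smoker |
| Both taken, both must pass | smoker |

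**2. Timing, in days from the quit date.** Assume patches start on day 0; six weeks then end on day 42.

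- MT: the quit date is session 4 of 8, twice weekly, so sessions end about day 14. Adding 2 weeks gives day 28.
- CM: three weeks of contacts end on day 21. Adding 2 weeks gives day 35.
- The other stated times, 4 weeks (if counted from the quit date) and 1 month, are about days 28 and 30.
- All fall before day 42. Overlap disappears at day 28 if patches start 14 or more days before the quit date (42 − 14 = 28), and at day 35 if 7 or more days before (42 − 7 = 35).
- The 3-month visit, about day 90, falls 90 − 42 = 48 days after the supply ends.

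**3. Size at 1 month.** All inputs are assumed. Let s be the share of true quitters judged by saliva alone or by a saliva veto, p the share of true quitters with patch cotinine above 30 ng/mL at the visit, and T the true abstinence rate. Taking s and p as independent, the misclassified share is f = s × p and observed abstinence is T × (1 − f).

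| s | p | f | Observed, T = 30% | Observed, T = 15% |
|---|---|---|---|---|
| 0 | any | 0 | 30% | 15% |
| 0.25 | 0.25 | 0.0625 | 28.1% | 14.1% |
| 0.5 | 0.5 | 0.25 | 22.5% | 11.3% |
| 1 | 0.5 | 0.50 | 15% | 7.5% |

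Per 100 enrolled, true quitters classed as smokers number 100 × T × f: 0, 1.9, 7.5 and 15 at T = 30%.

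**4. Between arms.** Take 50 per arm, T = 30% in both, p = 0.5, and s = 0 in one arm.

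- s = 0.25 in the other arm: 0.300 − 0.2625 = 0.0375; SE = √(0.30×0.70/50 + 0.2625×0.7375/50) = 0.090.
- s = 0.5 in the other arm: 0.300 − 0.225 = 0.075; SE = √(0.30×0.70/50 + 0.225×0.775/50) = 0.088.

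If f is the same in both arms, no false gap appears.

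**5. Stage 2.** Suppose that the verified status defines non-response, that 3-month abstinence is 20% (Switch) and 10% (Continue) in true non-quitters and 70% in misclassified quitters, and that the split is equal. At T = 30% the pool is N = 70 + 30f, of which c = 30f/N are misclassified. The Switch minus Continue difference is 0.10 × (1 − c).

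| f | N | c | Difference (points) | SE (points) |
|---|---|---|---|---|
| 0 | 70 | 0 | 10.0 | 8.5 |
| 0.0625 | 71.9 | 0.026 | 9.7 | 8.7 |
| 0.25 | 77.5 | 0.097 | 9.0 | 9.1 |
| 0.50 | 85 | 0.176 | 8.2 | 9.3 |

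The largest shift is 0.0176/0.0931 = 0.19 SE.

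**The case against.** The strongest reply is that the ordinary meaning of the wording is that either passing test confirms abstinence. With CO taken, an abstinent patch user passes. The CM text points the same way, since CO is the sample it names for verifying status. Saliva-only visits are permitted but not shown to be planned, and a saliva veto is only something the text fails to exclude. This stands as far as it goes: under that reading this error is absent. It does not close the gap, because nothing requires CO at the outcome visit and the CM wording governs reward samples.

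A second reply is that CO may miss some smoking within the 7 days, so the same loose rule can also overstate abstinence. That is correct. A reader might infer that the plan's 1-month rate is too low on balance. The documents do not support this; the net direction of all verification error is unknown.

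A reader might also infer bias between arms, because kit mailing is described only for CM. The assessment paragraph plans remote CO and/or saliva collection for all participants who report quitting, so MT participants must obtain a kit somehow. Silence on mailing does not show a different test mix, and even the assumed gaps in step 4 are below one SE.

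**Conclusion.** The concern holds as a defect in the 1-month verification rule. A visit conducted as the plan permits can class an abstinent patch user as a smoker on a primary outcome. It rests on two conditions: saliva alone, or a saliva veto, decides for some participants; and patches are in use near the visit, which assumes a start at or near the quit date.

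Its size is not derivable from the documents. The assumed range runs from no effect to a halving of the observed rate. The 3-month outcome is largely unaffected, apart from anyone using additional nicotine replacement then.

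A reader might go further and conclude that the Stage 2 comparison is compromised. The documents do not support that: they do not say that non-response means the verified outcome, and under the assumptions used the dilution is at most about 0.19 SE. The point deserves correction because the remedy is cheap, but it does not undermine the design.

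**What to change.** In the outcome definition and the matching collection text in section 5, apply one rule to both arms:

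1. Collect CO from everyone who reports abstinence at 1 month.
2. For anyone reporting NRT or other nicotine product use within a window fixed in advance (for example, the same 7 days), self-report plus CO below 8 ppm decides, and saliva cotinine does not overturn it.
3. If CO cannot be obtained from such a participant, a passing saliva test confirms abstinence. A failing one counts as missing verification, handled by the missing-data methods in section 7 (Data Management), with a sensitivity analysis counting missing as smoking.
4. Ask about NRT use explicitly at the 1-month visit, record which test was used, and report 1-month abstinence by test used.

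**Cost.** Protocol wording, an explicit question and one new field, plus making sure that MT participants have the CO device by the 1-month visit. CO covers a shorter window than cotinine, and a smoker who reports patch use avoids the cotinine check, so some smoking may be missed. The documents give no figure for this.

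**Separate points to reconcile, with no rule proposed here.** These are disagreement between tests in participants not using nicotine products, the meaning of not having quit for Stage 2, the differing visit timings, and the CM reward wording.
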